2.3 Study Drug: 3K3A-APC

3K3A-APC is a 405-residue protein expressed via recombinant technology in Chinese hamster ovary (CHO) cells. Its amino acid sequence differs from that of the wild-type human Activated Protein C (APC) and of the product drotrecogin alfa (activated) (Xigris[®]) in that 3 sequential lysine residues have been replaced with 3 sequential amino-acid substitutions (all lysine to alanine); the amino acid substitutions are K191A-K192A-K193A. This change retains the cytoprotective effects of native (wild-type) APC while significantly reducing its anticoagulant effects. Glycosylation of 3K3A-APC product differs from wild-type APC since it is expressed in CHO cells.

An important goal in the development of therapeutics intended for the treatment of acute stroke is to minimize bleeding risk while maximizing efficacy. 3K3A-APC is an APC variant that has been genetically engineered to maximize neuro- and cytoprotective activity and minimize anticoagulant activity. 3K3A-APC was developed by altering factor Va binding exosites (reducing anticoagulation) in APC without affecting exosites that recognize PAR1.

In *in vitro* assays, 3K3A-APC retains the cytoprotective activity of recombinant wild-type (rwt) APC but has < 10% of its anticoagulant activity (e.g. see Table 2 below²¹).

 Table 2:
 Cytoprotective and Anticoagulant Activity of rwt-APC versus 3K3A-APC

APC Type	Anticoagulant Activity (% rwt) ¹	Cytoprotective Activity (% rwt) ²	Cytoprotective to Anticoagulant Ratio
rwt-APC	100	100	1.0
3K3A-APC	4.6	114	25

¹Based on the activated partial thromboplastin time (aPTT) dose-response

²Derived from the concentrations of APC required for half-maximal inhibition of apoptosis induced by the protein kinase inhibitor, staurosporine

2.3.1 Rationale for APC in Treating Stroke

APC is an endogenous serine protease with systemic anticoagulant, anti-inflammatory, and antiapoptotic activities²². APC's anticoagulant activity is independent of its cellular effects. Its anticoagulant activity is mediated by irreversible proteolytic degradation of factors Va and VIIIa with contributions by various cofactors, whereas its cytoprotective activities are mediated by proteolytic activation of protease activated receptor 1 (PAR1)²³. Both properties (anticoagulant and cytoprotective) may be useful in reversing the effects of an ischemic stroke (via thrombolysis) and in protecting the ischemic brain tissue from further damage. APC's cellular signaling results in cytoprotective alterations in gene expression profiles resulting in anti-inflammatory activity and antiapoptotic activity²⁴⁻²⁸. APC is generated from zymogen protein C that is activated by thrombin on the surface of endothelial cells. The activation requires 2 membrane receptors, thrombomodulin and endothelial protein C receptor (EPCR) (Figure 2).

[figure not shown]

Figure 2: Blood Coagulation and Protein C Pathway

As noted above, APC acts directly on vascular and neuronal cells to exert multiple cytoprotective effects, mediated by its interaction with EPCR and the effector receptor, PAR-1²³. Specifically, APC protects neurons and brain endothelial cells from ischemic injury and cell death caused by a variety of apoptotic pathways^{24,29-31}. Early post-ischemic administration of APC within 4 hours of an ischemic insult is neuroprotective in rodent models of transient ischemia^{24,32} and embolic stroke³³. Delayed APC administration beginning at 6 hours following ischemic insult with continued bolus dosing 24, 48 and 72 hours following insult, is neuroprotective and mediates brain repair (i.e., neovascularization and neurogenesis), suggesting a significant extension of the therapeutic window for APC intervention in postischemic brain³⁴.

2.3.2 Rationale for use of APC following tPA or Mechanical Thrombectomy

The most frequently used FDA approved treatment for stroke is thrombolysis with recombinant human tPA¹³. Certain mechanical devices have received FDA approval for clot retrieval, and as shown above, mechanical thrombectomy has been shown to be effective in certain patients as a stroke therapy. All patients who meet tPA or mechanical thrombectomy treatment criteria and who arrive to the hospital acutely will receive tPA (within 4.5 hours of onset) or mechanical thrombectomy (within 6 hours of onset) or both, as standard of care. Neuroprotection appears to work best if delivered within 6 hours and in the setting of recanalization/reperfusion³⁵. Thus, the best way to study putative neuroprotectants is to combine them with recanalization treatments, which, if successful, results in reperfusion of ischemic tissue.

The combination of tPA and 3K3A-APC raises potential safety concerns. However, in all likelihood, there will be no tPA circulating by the time the first dose of 3K3A-APC begins. Modeled PK data for

tPA administration in stroke are shown in Section 5.5.1. The terminal half-life of tPA is ~5 minutes and these modeled data predict that circulating levels of tPA are nearing 0 μ g/mL by 30 minutes following completion of the infusion. In this study, 3K3A-APC or placebo will be given 30-120 minutes following administration of tPA, and therefore little to no circulating tPA is expected to be present during infusion of the IMP.

Studies of wt-APC—which has greater anti-coagulant potential than 3K3A-APC—in combination with tPA provide safety reassurance. Despite having anticoagulant properties, wt-APC has been shown to reduce tPA-induced bleeding and neurotoxicity in preclinical models, probably due to the anti-inflammatory and anti-apoptotic activity previously discussed^{24,29,31,32,36}. There is, however, a theoretical concern that administration of 3K3A-APC following tPA could have deleterious effects on coagulation or clot lysis. The effects of tPA on the anticoagulant activity of 3K3A-APC have been studied using aPTT clotting assays in vitro; tPA at a concentration of 3 µg/mL had little to no effect on the anticoagulant activity of either wt-APC or 3K3A-APC (Figure 3). Since we expect tPA levels to be virtually undetectable at the time of 3K3A-APC administration, we expect there will be no additional prolongation of aPTT in this study.

[figure not shown]

Figure Key: (**A**) Prolongation of the aPTT assay beyond the baseline reference clotting time of 47 sec was determined for plasma-derived wt-APC (open symbols) and for 3K3A-APC (solid symbols) when tPA was present at 0 (circles, solid lines) or $3.0 \ \mu\text{g/mL}$ (squares, dashed lines). Data show difference between observed aPTT value and control value of 47 sec. (**B**) The influence of tPA on the anticoagulant activity of 3K3A-APC was determined at the indicated concentrations (0, 45, 90, 140 nM). The tPA concentrations ($\mu\text{g/mL}$) were as follows: 0 (black bar), 0.5 (\square), 1.0 (red bar), 3.0 (blue bar). Data show observed aPTT values.

The effects of 3K3A-APC on the fibrinolytic activity of tPA has also been studied in vitro; no statistically significant effects on the ability of tPA to induce clot lysis were observed by either wt-APC or 3K3A-APC³⁷. Thus, we expect no impact on clot lysis in this study, either.

In summary, ischemic stroke patients who are eligible to receive tPA or mechanical thrombectomy or both are the most likely patient population to benefit from a neuroprotectant like 3K3A-APC, due to the need for reperfusion. Circulating tPA is cleared quickly from the body and levels are expected to be nearly undetectable by the time 3K3A-APC will be administered. Even so, in vitro studies show that there is minimal effect on 3K3A-APC coagulation and no significant effect on tPA clot lysis when both drugs are present at clinically relevant doses.

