5.4 Administration of Study Drug

Study drug will be infused into a large bore peripheral arm vein at a rate of 400 mL/hr over 15 minutes for all dose levels. The first dose of study drug will be administered 30 to 120 minutes after tPA has completed or mechanical thrombectomy begins (arterial puncture), whichever is sooner. Subsequent doses of study drug should be given every 12 hours (+/- 1 hour) for 5 total doses (or until discharge, whichever occurs first). It is preferable not to skip doses of study drug, and should a dose need to occur outside of the +/- 1-hour window (which will be reported as a protocol deviation), doses should never be given within 8 hours of one another. Please note that PK samples should be drawn from the opposite arm. See 'Drug Storage, Handling and Administration Manual' for further instructions on administration.

After the study drug infusion is complete, the IV line should be flushed with at least 20 mL of normal saline to ensure complete administration of the residual study drug. The calendar date, 24-hour clock time of the beginning and end of the infusion, and the volume infused should be recorded for capture in the CRF.

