- ¹² **CBC:** Perform a complete blood count with platelets; a differential must be performed if the white blood cell count is elevated (above the site's ULN).
- ¹³ Coagulation: Perform aPTT, PT, INR and fibrinogen. For each 3K3A-APC dose, samples should be drawn and processed pre-dose (window varies; see below) and 1 hour post-dose (+/- 15 minutes). For doses 2-5 the pre-dose window is within 60 minutes prior to the start of the infusion. For dose 1 however, note that some of these pre-dose assessments are required for screening and they should all be prior to tPA (in those subjects who receive tPA). Therefore, the pre-dose draw for dose 1 may be more than 60 minutes prior to the infusion. If the pre-dose samples for dose 1 are drawn after tPA they should not be drawn until at least 20 minutes has passed since tPA finished so as to minimize tPA's effect on the laboratory results.
- ¹⁴ **Urinalysis:** Microscopic urinalysis must be performed if dipstick is positive for RBCs.
- ¹⁵ **Pregnancy Test:** Serum or urine pregnancy test for women of child-bearing potential only.

¹⁶ **ECG**: One post-dose ECG should be collected at 'end of infusion' (Cmax) (+ 5 minutes). The Investigator can decide which dose, 1-5, will be used for ECG collection.

- ¹⁷ PK Samples: PK samples will be collected from subjects at a subset of participating sites; samples will be collected following one of the doses of 3K3A-APC at the following time points: end of infusion, 20, 40, 60 and 80 minutes post-dose. The Investigator can decide which dose, 2-5, will be used for PK collection.
- ¹⁸ Study Drug Administration: 3K3A-APC (or placebo) will be administered as a 15-minute infusion every 12 hours for 5 doses, or until discharge. The first dose of study drug (or placebo) should be started 30 to 120 minutes following completion of tPA or initiation of mechanical thrombectomy (arterial puncture), whichever occurs sooner. Subsequent doses should be given every 12 hours (+/- 1 hour) for 5 total doses (or until discharge). Dose 1 must be confirmed in the data system within 2 hours of infusion time.
- ¹⁹ SAE and Con Med Collection after Day 7: SAEs will be collected and reported out to actual study Day 30. Should a SAE be reported between Day 7 and Day 30, then all Con Meds through Day 30 need to be reported in the eCRF.

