6.3.1.3 Slot Assignment and Randomization

Following consent of the subject, or his/her legally authorized representative, the following assessments should be performed:

- Estimated pre-stroke mRS (to determine study eligibility)
- A pregnancy test in women of child bearing potential (serum or urine, per Investigator's discretion) will be required to qualify the eligibility of female patients.
- An actual pre-dose weight for each subject is preferred, as all investigational doses will be based on this weight. If a subject's weight was estimated for the purposes of study drug dose calculation, then an actual weight must be obtained within 24 hours of dose 1.

Subjects who have signed consent (or whose representatives have provided surrogate consent) and meet all inclusion and exclusion criteria can be randomized into the study; randomization will be managed electronically via the IWRS. The Investigator, or designee, should randomize the subject in the IWRS to receive the unique subject number, which will also be linked to the allocated treatment assignment (blinded to clinical staff). Subjects who will receive mechanical thrombectomy only should be randomized close to the start of the procedure (arterial puncture) to ensure that they continue to meet eligibility.

The unblinded pharmacist(s) will receive the treatment assignment from the IWRS that will be used to prepare the investigational treatment as described in Section 5.3.

It is important to confirm eligibility again close to investigational dose 1 as the NIHSS score may drop below 5 during the time between randomization and the first dose of study drug. For this reason, a repeat NIHSS should be assessed:

- Immediately prior to Dose 1 infusion if the subject received tPA treatment only, or
- Immediately prior to draping the subject in preparation for mechanical thrombectomy if the subject is to receive mechanical thrombectomy alone or in combination with tPA.

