6.3.2.1.2 Study-Specific Post-Treatment Procedures

Investigational Dose #1:

The first investigational dose of study drug should be started 30 to 120 minutes following completion of tPA or initiation of mechanical thrombectomy (arterial puncture), whichever occurs sooner.

After administration of 100 mL of investigational treatment, the following should be performed:

• Vital signs (blood pressure, heart rate, temperature, respiratory rate, oxygen saturation) should be collected at end of infusion (EOI) and approximately every hour (+/- 30 minutes) for 4 hours, then per local SOC. Temperature at EOI is not required.

NOTE: the NINDS tPA protocol should guide vital sign collection following tPA administration; therefore, actual collection may be more frequent than what will be captured for this study protocol. The eCRF will capture one hourly time point for the first 24 hours. For subjects who undergo mechanical thrombectomy only, one hourly time point for the first 24 hours must be captured.

- Blood for coagulation (PT, aPTT, INR, fibrinogen) should be collected 1 hour after EOI (+/-15 minutes).
- One post-dose ECG should be collected at EOI (C_{max}) (+ 5 minutes). The Investigator can decide which dose, 1-5, can be used for ECG collection. Since the ECG collection is flexible, it should be planned well in advance so that it is collected as close to EOI as possible. Should the ECG window be missed, it is preferred to defer the collection to the next planned investigational dose.

Investigational Doses #2-5:

Subjects should receive 100 mL of investigational treatment every 12 hours (+/- 1 hour) for up to 5 total doses (refer to section 5.4). Subjects will only receive investigational treatment for as long as they remain as an inpatient. The following should be performed:

- Vital signs should be collected just prior to infusion, at EOI and approximately every hour (+/- 30 minutes) for 4 hours, then per local SOC
- Blood for coagulation (PT, aPTT, INR, fibrinogen) should be collected from the arm opposite the infusion:
 - Prior to each infusion (within 60 minutes of infusion)

- 1 hour after EOI (+/- 15 minutes)

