Four dose levels will be considered for this study: 120, 240, 360, and 540 µg/kg. Following completion of tPA infusion, or initiation of mechanical thrombectomy (arterial puncture), whichever is sooner, eligible adult subjects will receive 3K3A-APC or placebo 30 to 120 minutes later given as a 15 minute infusion. Subjects will receive another 15 minute infusion of study treatment every 12 hours (+/- 1 hour) for up to 5 total doses (or until discharge, whichever occurs first). It is preferable not to skip doses of study drug, and should a dose need to occur outside of the +/- 1 hour window (which will be reported as a protocol deviation), doses should never be given within 8 hours of one another.

For the purposes of this study, we assume an established background symptomatic intracerebral hemorrhage (SICH) rate of 3-6% (Wahlgreen et al, 2007; Hacke et al, 2008; Berkhemer et al, 2015; Campbell et al, 2015; Goyal et al, 2015; Saver et al, 2015). Correspondingly, this study aims to identify the highest dose with a DLT rate of 10% or less. Subjects will be enrolled to 3K3A-APC dose cohorts in groups of four (three to specified treatment dose and one to placebo). Subjects will generally be enrolled at the dose estimated from the model at that time, based on the assumed original dose-response model and all prior observed data to date, as the highest dose with a DLT rate of 10% or less. However, the initial cohort will start at the lowest dose (120 µg/kg) and the dose level may be escalated by no more than one dose between consecutive cohorts (there are no restrictions on dose level de-escalation). Intra-subject dose modification is not permitted during the study. After the final group of subjects is enrolled, the final MTD will be defined as the highest dose with an estimated toxicity probability less than or equal to the target toxicity level of 10%.

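### In patients who get both tPA and thrombectomy, the first-dose timing rule does not guarantee the tPA washout that the safety rationale describes

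*Protocol*

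**What the plan says.** **Rationale.** Protocol 2.3.2 acknowledges that combining tPA with 3K3A-APC raises potential safety concerns. Its first answer is timing: "in all likelihood, there will be no tPA circulating by the time the first dose of 3K3A-APC begins". It describes the schedule this way: "In this study, 3K3A-APC or placebo will be given 30-120 minutes following administration of tPA". From that it concludes: "therefore little to no circulating tPA is expected to be present during infusion of the IMP". It also expects no additional aPTT prolongation, because tPA should be almost undetectable.

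**Timing rule.** Protocol 5.4 sets the first dose at "30 to 120 minutes after tPA has completed or mechanical thrombectomy begins (arterial puncture), whichever is sooner". The same rule stands in the Synopsis, 3.1, 6.1 (footnote 18), 6.2 (footnote 16), 6.3.2.1.2 and 8.1.1. SAP 1 has it too: "Following completion of tPA infusion, or initiation of mechanical thrombectomy (arterial puncture), whichever is sooner".

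**Population.** The title and objectives include patients who receive both treatments. Protocol 6.3.1.3 gives them a specific step, a repeat NIHSS before draping "if the subject is to receive mechanical thrombectomy alone or in combination with tPA". I found no passage that requires tPA to be finished, or a minimum gap after it, before dose 1 in these patients.

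**Coagulation baseline.** Samples before dose 1 should precede tPA. If they were not drawn by then, "they should not be drawn until at least 20 minutes has passed since tPA finished" (Protocol 6.1, footnote 13; repeated in 6.2, footnote 11, and in 6.3.1.1.1).

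**The concern.** The rationale counts time from one event, the end of tPA. The rule counts from the earlier of two events. The two agree for a patient who gets tPA only. They part when the artery is punctured while tPA is still running: the clock then starts before tPA has finished, and the 30-minute gap that the rationale relies on is shortened or lost.

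At stake is the reading of bleeding events. Symptomatic intracranial hemorrhage and other serious bleeding are DLT components (Protocol 3.1.1, 8.2.1; SAP 2). DLTs drive the dose-finding model, and each cohort adds only three treated subjects. A bleed in a patient exposed to both drugs at once is harder to attribute than one after washout, and nothing in SAP 10 shows which patients were in which position.

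**Working it through.** **Inputs.** Protocol 5.5.1 gives the tPA model: one compartment, clearance (CL) about 475 mL/min, half-life about 5 minutes, and 9 mg in the first minute followed by 81 mg, for 60 minutes in all. Study drug runs for 15 minutes (Protocol 5.4). The documents give no distribution of puncture times, so those below are assumptions. Time is counted from tPA start.

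**Reproducing the plan's figures.**
- Volume: V = CL × t½ / ln 2 = 475 × 5 / 0.693 = 3,426 mL (stated: about 3,400).
- Rate constant: k = 0.693 / 5 = 0.1386 per minute.
- Steady state: 81,000 µg / 59 min / 475 mL/min = 2.89 µg/mL (stated: 2.9).
- After the first minute: (9,000 / 475) × (1 − e^−0.1386) = 2.45 µg/mL. The level then rises to 98.9% of steady state at 20 minutes and 99.5% at 25 (stated: steady state by 20 to 25 minutes).
- 30 minutes after tPA ends, six half-lives: 2.89 / 2^6 = 2.89 / 64 = 0.045 µg/mL (stated: nearing 0).

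**Earliest dose 1 under the timing rule.** Earliest start = min(puncture time, 60) + 30. After minute 60, C(t) = 2.89 × 2^−((t − 60)/5). For a dose starting at minute 60 or later, the mean over its 15 minutes is C(start) × (1 − 2^−3) / (15k) = 0.421 × C(start).

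| Puncture (min) | Earliest dose 1 (min) | Overlap with running tPA (min) | tPA at dose start (µg/mL) | Mean over study drug infusion (µg/mL) |
|---|---|---|---|---|
| 10 | 40 | 15 | 2.89 | 2.89 |
| 15 | 45 | 15 | 2.89 | 2.89 |
| 20 | 50 | 10 | 2.89 | 2.62 |
| 25 | 55 | 5 | 2.89 | 2.01 |
| 30 | 60 | 0 | 2.89 | 1.22 |
| 40 | 70 | 0 | 0.72 | 0.30 |
| 45 | 75 | 0 | 0.36 | 0.15 |
| 60 or later | 90 or later | 0 | 0.045 or less | 0.019 or less |

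Overlap with the running infusion needs puncture less than 30 minutes after tPA start. The full 30-minute gap can be lost whenever puncture comes before tPA ends.

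**The 1-hour aPTT sample.** It is drawn 1 hour ± 15 minutes after the end of the study drug infusion (Protocol 6.3.2.1.2). The least favorable case with puncture at or after tPA start is puncture at 0, dose at 30, end of infusion at 45 and draw at 45 + 45 = 90. That is 30 minutes after tPA ends, at 0.045 µg/mL, the level that the rationale itself accepts. For puncture at 10 and a nominal draw, the sample falls at 10 + 30 + 15 + 60 = 115 minutes, with tPA at 2.89 / 2^11 = 0.001 µg/mL.

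**The 20-minute draw rule.** A compliant late draw is possible from 60 + 20 = 80 minutes. The dose window runs from puncture + 30 to puncture + 120. Puncture at 0 gives 30 to 120, and puncture at 10 gives 40 to 130. Both leave room after minute 80. The rule therefore conflicts only with dosing before minute 80, and only if coagulation was not drawn before tPA.

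**The case against.** The best answer is that the protocol does not rest on timing alone. Section 2.3.2 reports in vitro work in which tPA at 3 µg/mL, about the modeled steady state, had little or no effect on the anticoagulant activity of 3K3A-APC. It also reports no significant effect on tPA-induced clot lysis. Section 2.4.1 describes rodent studies of tPA combined with 3K3A-APC in which tPA-related microhemorrhages were eliminated. The timing claim is itself worded as an expectation. The Safety Review Committee adjudicates every suspected DLT and can set aside one that is definitely due to another cause; a tPA effect is one of the named examples.

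Most of this stands, and it lowers the stakes. A reader might infer that co-exposure is unsupported by any evidence; the documents do not bear that out. The evidence has limits, though. It is in vitro and animal evidence, and 3 µg/mL lies below the protocol's own upper limit for tPA protein (about 4.5 µg/mL, section 5.5.1), though above its limit for activity (about 2.3 µg/mL). It also does not make the timing statement true for patients who get both treatments. Committee review is case by case and gives no view across patients.

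Two other strong readings are tempting. One is that overlap contaminates the 1-hour aPTT DLT. The arithmetic above shows that the sample is largely unaffected. The other is that the 20-minute draw rule cannot be met in these patients. It can, within the 120-minute window; it fails only when dosing comes earlier than 20 minutes after tPA ends.

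**Conclusion.** The rationale and the timing rule contradict each other for patients who receive both treatments. The rule permits dose 1 to begin at a modeled tPA level of about 2.9 µg/mL, some 64 times the 0.045 µg/mL in the case that the rationale describes, or at about 0.36 µg/mL (8 times) with puncture at 45 minutes. These ratios refer to dose start at the earliest permitted minute. They rest on the protocol's one-compartment model, which was extrapolated from myocardial infarction data, and on assumed puncture times.

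A reader might infer that overlap is routine. The documents do not support that. It needs both treatments, early puncture and dosing early in the window, and later dosing in the same window can follow washout. The share of patients affected cannot be worked out from the documents.

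What remains is more than a wording slip. A stated safety property is not delivered by the rule that governs dosing, and it bears on the attribution of bleeding and symptomatic intracranial hemorrhage DLTs.

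**What to change.** **Protocol.** The sponsor must reconcile section 2.3.2 with the timing passages (Synopsis, 3.1, 5.4, 6.1, 6.2, 6.3.2.1.2, 8.1.1; SAP 1) and with the 20-minute draw rule. Which text should change is a clinical decision, and no dosing rule is proposed here.

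**SAP 10.** Add a descriptive listing, by treatment group, of DLTs, symptomatic intracranial hemorrhage and serious bleeding in patients given tPA. Split it by whether dose 1 began before tPA completion or less than 30 minutes after it, against 30 minutes or more after it.

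**Data.** Study drug start and end times are recorded (Protocol 5.4). SAP 5 uses tPA initiation and skin puncture times, and Protocol 6.4.3 sends tPA and device treatment to the eCRF. None of these names a tPA end time, so its capture must be confirmed.

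**Cost.** A text clarification and one small listing. With at most 66 planned active subjects (22 cohorts × 3) over four doses, cells will be sparse. The listing is for description only, with no test attached.
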